6.1. Summary

All study data will be uploaded or manually entered (as appropriate) onto REDCap, a secure web-based application for research data capture, management and analysis (hosted on the University of Melbourne data centre infrastructure, provided via the National eResearch Collaboration tools and Resources project).

The co-investigator, [name], will be responsible for ensuring that data are properly recorded and that all hard copy documents are securely stored.

Any protocol deviations will be documented and must also be reported to the Principal Investigator. Any actions arising from the protocol deviation will also be noted. Deviations identifying issues for protocol review will be amended as per Section 9.4.

6.2. Data Collection

Source documents in this study will include participants' ophthalmic records, relevant medical records, completed questionnaires, the patient study files (case report forms, CRFs), as well as the results of any diagnostic tests, such as blood tests and systemic fatty acid profiles.

Identifiable information will be collected and stored in a separate password-protected file that is only accessible to study investigators. The following data and information will be recorded:

- Identifiable participant information at baseline: name; contact details; study enrolment date
- A statement that written informed consent (including the date) was obtained prior to any study procedures being performed
- Participant ID number
- · Dates of all study visits
- Demographic information at baseline (age, sex, date of birth, ethnicity)
- Height and weight at baseline
- Medical and ophthalmic histories at baseline
- Pre-study and concomitant medications, including insulin type, administration method and dosage
- Study procedures performed at the University of Melbourne (UoM)
 - Habitual distance refractive correction in each eye at baseline.
 - Habitual distance visual acuity in each eye at baseline, day 30 ± 14 , day 90 ± 14 and day 180 ± 24 .
 - EQ-5D-5L questionnaire score at baseline, day 30 ± 14 , day 90 ± 14 and day 180 ± 24
 - Ocular Surface Disease Index (OSDI) questionnaire score at baseline, day 90 ± 14 and day 180 ± 24 .
 - Tear osmolarity in each eye at baseline and day 180 ± 24 .
 - Corneal sensitivity thresholds in the right eye at baseline, day 90 ± 14 and day 180 ± 24 .
 - Phenol red thread test score in each eye at baseline, day 90 ± 14 and day 180 ± 24 .

nPROOFS1-v1.2 [01-July-2018] Page 20 of 53

- Tear collection time and volume collected at baseline and day 180 ± 24 .
- Slit lamp examination gradings in each eye at baseline, day 90 ± 14 and day 180 + 24.
- Intraocular pressure (IOP) in each eye at baseline and day 180 ± 24 .
- Diabetic retinopathy (DR) and diabetic macular oedema grading (Wisconsin classification) in each eye at baseline and day 180 ± 24 .
- Optical coherence tomography angiography (OCT-A) imaging at baseline and day 180 ± 24 .
- Corneal sub-basal nerve plexus and dendritic cell parameters, measured using *in vivo* confocal microscopy (IVCM) in the right eye at baseline, day 90 ± 14 and day 180 ± 24 .
- Systemic fatty acid concentrations at baseline and day 180 ± 24 .
- Study procedures performed at St Vincent's Hospital Melbourne (SVHM)
 - Michigan Neuropathy Screening Instrument (MNSI) and Michigan Diabetic Neuropathy Score (MDNS) examination score at baseline and day 180 ± 24.
 - Nerve conduction study (NCS) parameters for the median motor, peroneal motor, tibial motor, median sensory, sural sensory, ulnar sensory nerves at baseline and day 180 ± 24 .
 - Cutaneous silent periods (CSP) measurements of the upper and lower limbs at baseline and day 180 ± 24 .
 - Quantitative Sudomotor Axonal Reflex Test (QSART) measurements of the forearm, proximal leg, distal leg and foot at baseline and day 180 ± 24 .
- Blood test results
 - Blood pathology test results at baseline and day 180 ± 24 .
 - Systemic fatty acid profiles at baseline and day 180 ± 24 .
- Occurrence, grading and status of any adverse events, including their potential association with the investigational product or a study procedure
- Number and proportion of supplements returned for each participant
- Participant's and examiner's forced-choice guesses of the treatment allocation (omega-3 PUFAs or placebo) on day 180 ± 24 .
- The date the participant exited the study, and a notation as to whether participant completed the study,

The co-investigator ([name]) and Principal Investigator will be jointly responsible for ensuring that data are properly transferred from CRFs and correctly recorded.

6.3. Data Management

6.3.1. Data coding

All data collected directly by the investigators for this study will be de-identified using a participant ID code, assigned to the participant when they sign the informed consent form. This ID code will be used as an identifier on all study documentation, and be used for the labelling of body tissue samples (i.e., blood, tears), which are processed off-site. The only individuals who will have the capacity to identify the participant's study results (by having access to the code linking the participant ID code to the participant's identity) will be the investigators listed on this application, and the participant themselves. The data will not be identifiable to any other persons.

6.3.2. Security and storage of data

Study data will be collected in both paper (hard copy) files and electronic formats.

For paper source documents, de-identified data, recorded during study examinations, will be stored in a binder (marked with the participant's ID code), and subsequently entered into the REDCap database (using each participant's ID code). The paper study source documents will be kept in a locked research room – The [name] Laboratory within the Department of Optometry and Vision Sciences, accessible only by research staff and students of the [name] Laboratory.

Data captured during study examinations in an electronic format will be labelled with the participant's ID code, and subsequently uploaded into the REDCap database. Only researchers name on the project application will have direct access to the raw study data.

6.4. Individual Data Reporting

Should a participant ask for details about the results of any of their study tests, immediate verbal feedback can be given by one of the study investigators. A report, summarising key findings relating to a participant's eye and/or peripheral nerve health, can also be made available, further to the participant's request, to potentially assist in guiding the participant's ongoing clinical care.

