3.7. Assignment of Interventions

3.7.1. Method of masking

Implementation of study allocation protocols will be conducted by an independent data manager. All trial participants and study investigators, including outcome assessors and data analysts, will be masked from the participant allocation.

Oral supplements will be packaged into identical opaque containers by a compounding pharmacist (Dartnell's Pharmacy, Surrey Hills, Victoria), to maintain double-masking. Participants' adherence to treatment will be monitored at follow-up visits by assessment of returned unused capsules by an independent researcher.

The investigators involved in the collection and analysis of data will not be involved in the reconciliation of returned study products, to maintain masking.

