9.7. Dissemination policy

A study summary to participants will be made available at the conclusion of the study. Participants will also be advised that they are welcome to phone or email the researchers if they are interested in receiving more information about any aspect of the research program.

Participants can request a copy of their individual study findings from the investigators; this information can either be provided verbally on the day, or in the form of a written report.

The findings from this study will be published as part of [name]'s PhD thesis and are also expected to be presented at relevant scientific meetings and/or submitted for publication to refereed journals. For the purpose of dissemination of the research results, all participants will be non-identifiable, as data are collated and averaged with the data of other participants in each group.

The full protocol, participant level dataset and statistical codes formed as part of this study will not be available for public access.

10. Study visit schedule and procedures

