10.5. Instructions to eligible participants

Eligible participants will be asked to attend a total of 6 study visits; four visits will be at the University of Melbourne, and two will be performed at St Vincent's Hospital (at the start and end of the supplementation period), within four weeks of the initial and final visits.

At Visit 1, eligible participants will be dispensed study products consisting of their randomised treatment allocation. Study investigators will counsel the participant to consume 2 capsules each day, with or without food, at least two hours before or after medications. Participants will be provided with a supplement log to document their consumption of capsules each day. Participants will be advised not to 'make up' for missed doses with additional capsules on a given day; a reason for a 'missed dose' should be documented on the supplement log, which will be returned along with any remaining capsules at Visits 3, 4 and 6.

An appointment will be arranged for participants within four weeks of Visit 1, to attend Visit 2 at St Vincent's Hospital, Melbourne. Participants will be asked to start their first dose on the day of Visit 2 (Day 1), following their assessments at St Vincent's Hospital. Participants will be advised that they should maintain their regular dietary habits and medications (including ocular and systemic) and notify us of any change in medications of dosage throughout the study.

Appointments for Visits 2 and 5 at St Vincent's Hospital will be arranged for the participants by the study investigators, at Visits 1 and 4 respectively.

Participants will be encouraged to contact the Principal Investigator at any time should they have any questions about the study or the instructions they have been given.

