11.1.10. Non-contact corneal aesthesiometry

At Visits 1, 4 and 6, corneal sensitivity will be measured using a non-contact corneal aesthesiometer (NCCA). Both room temperature and cooled air will be used to stimulate nerves with different sensory receptors in different locations of the cornea. The instrument will be positioned to fire a small stream of air, with a predetermined pressure (measured in mBar) as set by the examiner, from 1 cm away from the cornea. Both central cornea (i.e., half way between the temporal and nasal limbus) and inferior peripheral cornea (i.e., at 1mm above the most inferior limbus point) will be measured.

The participant will be seated comfortably on the slit lamp biomicroscope, where the instrument will be mounted, and asked to wear over-the-ear headphones, which will transmit a series of auditory cues to run each trial. The participant will also be given a small number pad with tactile pads to register their response to detecting a stimulus (i.e., yes and no).

The auditory cue consists of a short beep (0.5s) followed by a brief break (2s) and a long beep (4 seconds). For each individual trial, participants will be instructed that they should blink as frequently as they wish when they hear the first beep, but to stop blinking as soon as they hear the start of the second (i.e., long) beep as they may or may not feel a small stream of air during that time. The audio cue will be terminated by a double beep to indicate the end of the trial; after hearing this cue, the participant should register their response (i.e., yes or no) on the keypad.

The sensory threshold will be determined using a double-staircase threshold technique designed using a customised MATLab software. Trials will be repeated at discrete increments of 0.1 mbar for three reversals, until a final threshold can be calculated.

If participants respond 'yes' to two stimuli at 0.1 mbar, false positives will be checked by the examiner by initiating the testing sequence, but not releasing a stimuli. If participants respond 'yes' to two false positive checks, testing will stop, and the participants will be reinstructed. After instructions are given to the participant, testing will re-start from the beginning of the double staircase algorithm for that measurement.

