Appendix 1: nPROOFS1 Clinical Trial Protocol

At Visits 1, 4 and 6, corneal confocal microscopy will be performed to capture *in-vivo* images of the corneal sub-basal nerve plexus, using a Heidelberg Retinal Tomograph III with the Rostock Corneal Module (Heidelberg Engineering GmbH, Heidelberg, Germany). Topical anaesthesia will be instilled using the methods described above. A high-viscous eye gel (GenTealEyes. Novartis, North Ryde. NSW, Australia) will couple a single-use, sterile polymethylmethacrylate 'Tomocap' to the microscope objective lens.

Participants will be asked to fixate on a central target with the non-dominant eye while the right eye (i.e., same eye tested as NCCA) is examined. A sufficient number of images will be captures using "sequence" mode setting on the microscope of the central corneal region as a representation of that area. Participants will then be asked to fixate on a superior target while the inferior cornea (1mm above the inferior most limbus) will be imaged using the same methods as above.

Raw images will be saved on a secure server that is only accessible to the investigators. All captured images that are blurred, where the imaging depth was inconsistent, or where excessive vignette obstructs nerve visibility will be removed from the analysis sample. For each participant, 12 images from the central cornea and eight images from the peripheral cornea will be randomly selected for analysis. Images will be checked by the investigator to ensure that any overlap is kept minimal (i.e., less than 20%).

Central corneal sub-basal nerve parameters will be quantified using an automatic image analysis software (ACCMetrics software v2, The University of Machester) (Dabbah *et al.*, 2011). Sub-basal nerve parameters for each participant will be taken as the average value of the twelve images analysed for the following corneal nerve parameters: corneal nerve fibre length (CNFL; mm/mm²), corneal nerve fibre density (CNFD; fibres/mm²), corneal nerve branch density (CNBD; branches on main fibre/mm²) and corneal nerve total branch density (CTBD; total branches/mm²).

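### Sections 6.4 and 9.7 let participants learn post-baseline efficacy results on request during treatment, before the participant-dependent Day 180 outcomes are taken

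*Combined protocol and SAP*

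**What the plan says.** Protocol section 6.4 (Individual Data Reporting) covers a participant who asks for the results of "any of their study tests, immediate verbal feedback can be given by one of the study investigators". It adds that a written summary of key findings on eye and/or "peripheral nerve health, can also be made available", partly to help guide ongoing care. Section 9.7 (Dissemination policy) repeats the offer for individual findings: "this information can either be provided verbally on the day, or in the form of a written report". Neither section separates safety tests from efficacy outcomes or sets a visit before which efficacy results are withheld. Only the trial-level summary (section 6.5) waits for the end of the study.

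Section 3.7.1 (Method of masking) states: "All trial participants and study investigators, including outcome assessors and data analysts, will be masked from the participant allocation". Sections 3.7.1 and 3.7.2 deal with allocation, packaging, capsule counting and code breaks, and do not mention individual test results. Section 10.5 tells participants that "they should maintain their regular dietary habits and medications".

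Two corneal nerve tests fall in the middle of treatment. Section 11.1.18 says: "At Visits 1, 4 and 6, corneal confocal microscopy will be performed". Section 11.1.10 schedules aesthesiometry at the same three visits. In that test, after each trial, "the participant should register their response (i.e., yes or no) on the keypad".

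**The concern.** The plan protects participants' expectations with some care. It uses opaque containers, an independent capsule counter, an instruction about aftertaste meant to alter expectations (section 3.2), and treatment guesses at Day 180. On-request release of efficacy results during treatment is a route around these safeguards that no section closes.

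What is at stake are the outcomes that depend on the participant's own response after Visit 4:

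- **Key secondary:** central corneal sensitivity thresholds to room-temperature and cooled air, which are two of the four outcomes in the SAP's Benjamini-Hochberg family.
- **Secondary:** EQ-5D-5L index and VAS, and the questionnaire part of the MNSI.
- **Exploratory:** OSDI and the participant's guess of allocation.

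A participant who has been told that a nerve measure improved or worsened may answer differently, or change diet or adherence. The masking guess is also taken after any feedback, so on its own it could not separate a failure of masking from knowledge of results.

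**Working it through.** The plan gives no figure on this point, so the check sets the sections side by side and then sizes the clue.

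**1. Timing (section 10.4).** Visit 4 is Days 76 to 104 and Visit 6 is Days 156 to 204.

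- Shortest gap: 156 − 104 = 52 days.
- Longest gap: 204 − 76 = 128 days.

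**2. Which results exist before Visit 6.**

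| Test | Visits | Could a post-baseline result be known before Visit 6? |
|---|---|---|
| Aesthesiometry (11.1.10) | 1, 4, 6 | Yes. Software runs the staircase to a final threshold, so plausibly on the day |
| Confocal microscopy (11.1.18) | 1, 4, 6 | Only later. Images are screened, 12 are randomly selected and checked for overlap, then ACCMetrics is run and averaged |
| Limb nerve tests (11.2) | 2, 5 | None at Day 90. The Visit 5 result could be known if that visit comes first; 10.4 gives both visits the same window and 10.5 places them within four weeks of each other |
| Fatty acids (11.1.19) | 1, 6 | No |

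**3. How much a Day 90 result reveals.** Suppose a participant knows both the baseline and Day 90 CNFL and guesses omega-3 if it rose and placebo if it fell. With 1:1 allocation and normally distributed changes:

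P(correct) = ½ [P(rise | omega-3) + P(fall | placebo)]

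*Planning inputs* (section 2.4.1: difference 2.9 mm/mm², SD 3.2). Assumptions: 3.2 is the SD of change, and the mean placebo change is 0, so P(fall | placebo) = 0.5.

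- Half the difference reached by Day 90 (1.45): ½ [Φ(1.45/3.2) + 0.5] = 0.587, about 59%.
- All of it reached (2.9): ½ [Φ(2.9/3.2) + 0.5] = 0.659, about 66%.

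*Table S4, Day 90 change, mean (SD).*

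| Measure | Omega-3 | Placebo | P(rise, omega-3) | P(fall, placebo) | P(correct) |
|---|---|---|---|---|---|
| CNFL | 1.62 (1.92) | −0.15 (1.12) | 0.801 | 0.553 | 0.677 |
| CNFD | 2.78 (3.99) | 0.49 (3.19) | 0.757 | 0.439 | 0.598 |
| CNBD | 5.65 (8.23) | −2.84 (6.39) | 0.754 | 0.672 | 0.713 |

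Chance is 50%. Table S4 reports the sensitivity thresholds as medians and quartiles, so this calculation was not made for aesthesiometry, the one nerve measure plausibly available on the day.

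**The case against.** The strongest reply is that little of this is shown to happen. The wording is permissive and depends on a request. The investigator giving feedback is masked too, and section 3.7.1 masks allocation, not results. Confocal values need processing that no section places before Visit 6. Several routes to harm are watched: diet and medication changes are asked about at follow-up, adherence is checked by capsule count and fatty acids, a sensitivity analysis excludes non-compliers, and aesthesiometry has blank-trial checks when a participant twice answers yes at 0.1 mbar. In Table S4 the two central thresholds did not reach 0.05 at Day 180 (p = 0.061 and 0.077), whereas the automated central nerve measures did.

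Most of this stands as a limit on size. It does not close the route: monitoring diet and adherence does not address a change in how a participant answers, and a threshold p-value above 0.05 does not show that answers were unaffected.

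A reader might infer four stronger things that the documents do not support:

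- **That all nerve results are exposed at Day 90.** Limb and fatty-acid results do not exist then.
- **That the arm could be guessed about 74% of the time.** That figure needs a CNFL cut-off of about 1.06, fitted to the trial's own arm distributions, which no masked person could know. Even the 68% averages 80% on omega-3 with 55% on placebo.
- **That any shift must favour the arm difference.** Nothing in the documents establishes its direction.
- **That the primary outcome is compromised.** CNFL is quantified automatically, so any effect would be indirect, through adherence or dropout, and none is shown.

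**Conclusion.** The point holds as a gap in a stated rule. Sections 6.4 and 9.7 positively allow release of any test result during treatment, and no other section withholds post-baseline efficacy results. The direct exposure is at Visit 6, to participant-dependent outcomes that include two of the four key secondary outcomes.

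The clue is partial: about 59–66% correct guesses from the sign of the CNFL change with planning inputs, or about 68% with Table S4 values, against 50%. Those figures assume normal changes, knowledge of both baseline and Day 90 values, and confocal results reported before Visit 6. The planning range also assumes that 3.2 is the SD of change and that half to all of the difference is present by Day 90. How many participants asked is not stated, and no bias is shown to have occurred. The change is worth making because it is cheap; the gap does not undermine the primary analysis.

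**What to change.** In sections 6.4 and 9.7, and in the participant information, state that post-baseline efficacy results are released on request only after the participant has completed both Visits 5 and 6 or has exited. This covers Visit 4 confocal microscopy, aesthesiometry and other ocular efficacy measures, and the Visit 5 nerve function tests. Leave release of baseline results, safety results and any clinically important finding as it is now: baseline values precede dosing and carry no information on allocation, and section 6.4 offers reports to support care. Log any earlier disclosure so that it can be reported beside the masking guesses. Since the SAP dates the last participant's last visit to 10 March 2020, for this trial the practical step is to report whether such disclosures were made, and to how many participants, as far as source records allow.

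The cost is a sentence in each section and a log. Sample size, alpha and treatment are unchanged. The downside is that participants wait until the end of their own follow-up for non-safety, post-baseline results.

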6.5. Study summary

At the conclusion of the study, a study summary report will be made available to participants who indicate wishing to receive this report during the written informed consent process.

6.6. Retention of study documentation

All study related data, participant records, consent forms, patient privacy documentation, records of the distribution and use of all study products, and copies of case report forms will be maintained on file. Electronic data and paper files will be kept for a minimum of 15 years, but possibly longer if the data is judged of continuing value at that time.

7. Safety measures

